3.4.4 Capecitabine

Given that capecitabine is an FDA-approved agent, dose adjustments and management will be as per standard of care, as outlined in the package insert. Capecitabine will be withheld in cases of Grade 2 or greater hand-foot syndrome or mucositis that do not respond to medical management. Capecitabine will be restarted after the symptoms improved to Grade 1. The dose of Capecitabine may be adjusted in the event of recurrent Grade 2 or greater hand-foot syndrome, neutropenia, or other Capecitabine toxicities that have not been attributed to other study agents.

Summary of management of common Capecitabine toxicities	
Toxicity	Capecitabine dose modification
Grade 2 hand foot syndrome	Interrupt until \leq grade 1. May then restart capecitabine at full dose. For second occurrence, hold capecitabine until \leq grade 1, then restart capecitabine one dose level lower (75% of starting dose first occurrence, 50% of the starting dose the second occurrence, discontinue the third occurrence).
Grade 3 hand foot syndrome	Interrupt until \leq grade 1. Then restart capecitabine one dose level lower (75% of starting dose first occurrence, 50% of the starting dose the second occurrence, discontinue the third occurrence).

*Dose reductions for capecitabine

1. Starting dose
2. 75% of the starting dose
3. 50% of the starting dose

3.4.5 Oxaliplatin

3.4.5.1 Peripheral neuropathy

Oxaliplatin is consistently associated with two types of peripheral neuropathy, which includes paresthesia and dysesthesias of the hands, feet, and peri-oral region. Patients treated with oxaliplatin in this study will be counseled to avoid cold drinks and exposure to cold water or air, especially for 3 to 5 days following oxaliplatin administration.

3.4.5.1.1 Neurologic Toxicity Scale for Oxaliplatin Dose Adjustments

Description	Grade	1 st occurrence	2 nd occurrence	3 rd occurrence
Paresthesia/dysesthesias that do not interfere with function	1	no dose reduction	no dose reduction	no dose reduction
Paresthesia/dysesthesias, interfering with function, but not activities of daily living (ADL)	2	no dose reduction	no dose reduction	100 mg/m ²

Description	Grade	1 st occurrence	2 nd occurrence	3 rd occurrence
Paresthesia/dysesthesias b with pain or with functional impairment that also interfere with ADL	3	no dose reduction	100 mg/m ²	Stop treatment permanently
Persistent paresthesia/dysesthesias that are disabling or life-threatening	4	Stop treatment permanently	Stop treatment permanently	Stop treatment permanently
ACUTE: (during or after the 2-hour infusion) laryngopharyngeal dysesthesias		increase duration of next infusion to 6 hours	N/A	N/A

3.4.5.2 Laryngopharyngeal dysesthesias

An unusual laryngopharyngeal dysesthesia, a loss of sensation of breathing (acute respiratory distress) without any objective evidence of respiratory distress (hypoxia, laryngospasm, or bronchospasm), also has been observed. This neurotoxicity may be induced or exacerbated upon exposure to cold.

If a patient develops laryngopharyngeal dysesthesia, the patient's oxygen saturation should be evaluated via a pulse oximeter and, if normal, reassurance, a benzodiazepine or other anxiolytic agent should be considered and the patient should be observed in the clinic until the episode has resolved. The oxaliplatin infusion may then be continued at 1/3 the rate. Because this syndrome may be associated with the rapidity of oxaliplatin infusion, subsequent doses of oxaliplatin should be administered as 6-hour infusions (instead of the normal 2-hour infusion).

Patients on oxaliplatin should not receive cold drinks or ice chips on Day 1 of each cycle as this may exacerbate oral or throat dysesthesias, as well as laryngopharyngeal dysesthesia.

3.4.5.3 Allergic reactions

For Grade 1 or 2 acute hypersensitivity reactions, no dose modification of oxaliplatin is required if, in the investigator's opinion, it is in the patient's best interest to continue. Pre-medication with dexamethasone 20 mg IV, diphenhydramine 50 mg IV, and one of the following: cimetidine 300 mg IV, ranitidine 50 mg IV, or famotidine 20 mg IV 30 minutes prior to study drug administration is suggested. If an allergic reaction persists into the next cycle, administer 50 mg dexamethasone PO 12 hours and 6 hours prior to administration of oxaliplatin.

For Grade 3 or 4 acute hypersensitivity reactions, treatment with oxaliplatin should be discontinued.

3.4.6 Pembrolizumab

The following broad guidelines for dose delivery schedule delays and alternations apply to pembrolizumab and are dependent on the clinical and laboratory assessment on the day of dosing. Pembrolizumab can be delivered within 72 hours of planned interval to accommodate scheduling issues/logistics.

Based on the mechanism of action of pembrolizumab leading to T-cell activation and proliferation, there is the possibility of observing irAEs during the conduct of this study.

Potential irAEs may be similar to those seen with the use of ipilimumab, BMS-936558 (anti-PD-1 mAb), and BMS-936559 (anti-PD-L1 mAb) and may include immune-mediated enterocolitis, dermatitis, hepatitis (hepatotoxicity), and endocrinopathies[[6](#), [59](#), [60](#)]. These AEs are inflammatory in nature and can affect any organ.

Subjects should be monitored for signs and symptoms of irAEs. In the absence of an alternate etiology (e.g., infection or PD), an immune-related etiology should be considered for signs or symptoms of enterocolitis, dermatitis, hepatitis, and endocrinopathy. In addition to the dose modifications shown in **Table 1**, it is recommended that management of irAEs follow the guidelines outlined for ipilimumab[[81](#)]. These guidelines recommend the following:

1. Subjects should be evaluated to identify any alternative etiology
2. In the absence of clear alternative etiology, all events of an inflammatory nature should be considered to be immune-related
3. Symptomatic and topical therapy should be considered for low grade events (all Grade 1 events, dermatologic and pruritus Grade 2 events).
4. Systemic corticosteroids should be considered for a persistent low-grade event or for a more severe event
5. More potent immunosuppressives should be considered for events not responding to systemic steroids (e.g., infliximab, mycophenolate, etc.).

Dose modifications will not be required for AEs that are clearly not attributed to pembrolizumab (such as an accident) or for laboratory abnormalities that are not deemed to be clinically significant, or which are ascribable to CAPOX. Dose reductions of pembrolizumab are not permitted.

General guidelines regarding dose modification are provided in **Table 1**. All toxicities will be graded according to NCI CTCAE v4.0.

Dosing interruptions are permitted in the case of medical / surgical events or logistical reasons not related to study therapy (e.g., elective surgery, unrelated medical events, patient vacation, and/or holidays). Subjects should be placed back on study therapy within 3 weeks of the scheduled interruption. The reason for interruption should be documented in the patient's study record.

Table 1: Dose Modification Guidelines for Drug-Related Adverse Events, version 10-22-2017

General instructions:				
Immune-related AEs	Toxicity grade or conditions (CTCAEv4.0)	Action taken to pembrolizumab	irAE management with corticosteroid and/or other therapies	Monitor and follow-up
Pneumonitis	Grade 2	Withhold	
 Administer corticosteroids (initial dose of 1-2 mg/kg prednisone or equivalent) followed by taper 	
 Monitor participants for signs and symptoms of pneumonitis Evaluate participants with suspected pneumonitis with radiographic imaging and initiate corticosteroid treatment Add prophylactic antibiotics for opportunistic infections
	Grade 3 or 4, or recurrent Grade 2	Permanently discontinue		
Diarrhea / Colitis	Grade 2 or 3	Withhold	
 Administer corticosteroids (initial dose of 1-2 mg/kg prednisone or equivalent) followed by taper 	
 Monitor participants for signs and symptoms of enterocolitis (i.e., diarrhea, abdominal pain, blood or mucus in stool with or without fever) and of bowel perforation (i.e., peritoneal signs and ileus). Participants with \geq Grade 2 diarrhea suspecting colitis should consider GI consultation and performing endoscopy to rule out colitis. Participants with diarrhea/colitis should be advised to drink liberal quantities of clear fluids. If sufficient oral fluid intake is not feasible, fluid and electrolytes should be substituted via IV infusion.
	Grade 4	Permanently discontinue		
AST / ALT elevation or	Grade 2	Withhold	
 Administer corticosteroids (initial dose of 0.5- 1 mg/kg prednisone or equivalent) followed by taper 	
 Monitor with liver function tests (consider weekly or more frequently until liver enzyme value returned to baseline or is

Immune-related AEs	Toxicity grade or conditions (CTCAEv4.0)	Action taken to pembrolizumab	irAE management with corticosteroid and/or other therapies	Monitor and follow-up
Increased bilirubin	Grade 3 or 4	Permanently discontinue	
 Administer corticosteroids (initial dose of 1-2 mg/kg prednisone or equivalent) followed by taper 	stable
Type 1 diabetes mellitus (T1DM) or Hyperglycemia	Newly onset T1DM or Grade 3 or 4 hyperglycemia associated with evidence of β -cell failure	Withhold	
 Initiate insulin replacement therapy for participants with T1DM Administer anti-hyperglycemic in participants with hyperglycemia 	
 Monitor participants for hyperglycemia or other signs and symptoms of diabetes.
Hypophysitis	Grade 2	Withhold	
 Administer corticosteroids and initiate hormonal replacements as clinically indicated. 	
 Monitor for signs and symptoms of hypophysitis (including hypopituitarism and adrenal insufficiency)
	Grade 3 or 4	Withhold or permanently discontinue ¹		
Hyperthyroidism	Grade 2	Continue	
 Treat with non-selective beta-blockers (e.g., propranolol) or thionamides as appropriate 	
 Monitor for signs and symptoms of thyroid disorders.
	Grade 3 or 4	Withhold or permanently discontinue ¹		
Hypothyroidism	Grade 2-4	Continue	
 Initiate thyroid replacement hormones (e.g., levothyroxine or liothyroinine) per standard of care 	
 Monitor for signs and symptoms of thyroid disorders.
Nephritis and Renal dysfunction	Grade 2	Withhold	
 Administer corticosteroids (prednisone 1-2 mg/kg or equivalent) followed by taper. 	
 Monitor changes of renal function
	Grade 3 or 4	Permanently discontinue		
Myocarditis	Grade 1 or 2	Withhold	
 Based on severity of AE administer corticosteroids 	
 Ensure adequate evaluation to confirm etiology and/or exclude other causes

Immune-related AEs	Toxicity grade or conditions (CTCAEv4.0)	Action taken to pembrolizumab	irAE management with corticosteroid and/or other therapies	Monitor and follow-up
	Grade 3 or 4	Permanently discontinue		
All other immune-related AEs	Intolerable/persistent Grade 2	Withhold	
• Based on type and severity of AE administer corticosteroids	
• Ensure adequate evaluation to confirm etiology and/or exclude other causes
	Grade 3	Withhold or discontinue based on the type of event. Events that require discontinuation include and not limited to: Gullain-Barre Syndrome, encephalitis		
	Grade 4 or recurrent Grade 3	Permanently discontinue		

1. Withhold or permanently discontinue pembrolizumab is at the discretion of the investigator or treating physician.

NOTE:

For participants with Grade 3 or 4 immune-related endocrinopathy where withhold of pembrolizumab is required, pembrolizumab may be resumed when AE resolves to \leq Grade 2 and is controlled with hormonal replacement therapy or achieved metabolic control (in case of T1DM).

3.5 STUDY CALENDAR

	Screening	Baseline	Cycles 1-6⁵	Cycle 7- to PD⁵	EOT⁹	Follow Up¹⁰
Pembrolizumab ¹			X	X		
Oxaliplatin ²			X			
Capecitabine ³			X			
Informed consent	X					
Medical history ⁴	X	X				
Concomitant meds			X	X		
Adverse event evaluation			X	X	X	
Physical exam ⁴	X	X	X	X	X	
Vital signs ⁴	X	X	X	X	X	
Height	X					
Weight ⁴	X		X	X		
Performance Status ⁴	X		X	X	X	
CBC w/differential, Platelets ⁴	X		X ¹³	X ¹³	X	
PT, INR, PTT, Fibrinogen			X ¹³	X ¹³	X	
Serum chemistry ^{4, 12}	X		X ¹³	X ¹³	X	
HIV, Hepatitis B and C serology and/or viral load	X					
HLA		X				
Thyroid Panel			X ¹³	X ¹³	X	
TB testing (if clinically indicated)	X					
Serum or urine pregnancy test ⁴	X	X				

	Screening	Baseline	Cycles 1-6 ⁵	Cycle 7- to PD ⁵	EOT ⁹	Follow Up ¹⁰
Tumor markers: aFP, CEA or Ca 19.9 ⁴			X ¹³	X ¹³		
EKG ⁴	X	X				
Confirmation of dx by NCI LP	X					
Restaging radiologic Evaluation ⁴	X	X	X ⁶	X ⁶		
Optional Tumor biopsy		X	X ⁷			
Immune monitoring ¹¹			X	X		
Blood for TCR beta sequencing ¹⁴			X	X		
Advance Directive ⁸		X				
Annual telephone contact						X

¹ 200 mg of Pembrolizumab will be administered as a 30-minute IV infusion Day 1 of each cycle.

² Oxaliplatin will be administered on D1 of each cycle at a dose of 130mg/m² IV

³ Capecitabine will be administered at a dose of 750 mg/m² PO every 12 hours. Doses will be rounded downward to the nearest 150 mg. Patients will begin Capecitabine dosing on the Day 1 of each cycle and will continue to receive Capecitabine for 14 days.

⁴ Tests performed at screening do not need to be repeated on baseline or Cycle 1 Day 1 if performed in designated time frame

⁵ Each cycle is 21 days. Trial treatment may be administered up to 3 days before or after the scheduled Day 1 of each cycle due to administrative reasons.

⁶ CT/PET/MRI of chest abdomen and pelvis. Restaging scans every 9 weeks +/- 7 days.

⁷ Performed on cycle 3 Day 1 only +/- 7 days

⁸ As indicated in section **10.3**, all subjects will be offered the opportunity to complete an NIH Advance Directive form. This should be done preferably at baseline but can be done at any time during the study as long as the capacity to do so is retained. The completion of the form is strongly recommended but is not required.

⁹ The off-treatment visits/labs will occur if patient is agreeable to coming back and physically able to return for the visit. This visit may should occur around day 30 post the last dose of study drug. If toxicities cause discontinuation of therapy, patients will be followed until resolution of toxicity to at least Grade 1. If the patient cannot return to the Clinical Center for this visit, a request will be made to collect required clinical labs from a local physician or laboratory. If this is not possible, patients may be assessed by telephone for symptoms.

¹⁰ Follow-up will be annual telephone contact to assess survival status. Every attempt will be made to contact patient/subject including: contacting referring physician, contacting emergency contact patient identified on admission, checking SSDI (Social Security Death Index)

¹¹ Immune monitoring on Day 1 of cycles 1-4, then every 12 weeks until PD, +/-48 hours' time window applies

¹² Electrolytes, BUN, creatinine, AST, ALT, total and direct bilirubin, calcium, phosphorus, albumin, magnesium, uric acid, amylase. Uric acid and amylase do not need to be done on screening

¹³ Within 48 hours prior to study drug

¹⁴ D1 of each cycle until PD, +/-48 hours' time window applies

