2.2 SCREENING EVALUATION

Studies should be done within 28 days prior to enrollment unless otherwise noted below.

Note: Screening evaluation testing/procedures are conducted under the separate screening protocol, 01-C-0129 (Eligibility Screening and Tissue Procurement for the NIH Intramural Research Program Clinical Protocols).

- Complete medical history (including prior hormone use) and physical examination (including height, weight, vital signs, EKG, and ECOG performance status).
- Laboratory Evaluation
 - Hematological profile: CBC with differential and platelet count.
 - Biochemical profile: electrolytes, BUN, creatinine, AST, ALT, total and direct bilirubin, calcium, phosphorus, albumin, magnesium,
 - Serum or urine pregnancy test for female participants of childbearing age (in the absence of prior hysterectomy).
 - HIV, Hepatitis B and C serology and/or viral load
 - TB testing (if clinically indicated)
- CT or PET of chest, abdomen and pelvis (or MRI abdomen)
- Histologic confirmation (at any time point prior to enrollment). A block or unstained slides of primary or metastatic tumor tissue will be required from each participant to confirm diagnosis with analysis being performed by the Laboratory of Pathology, NIH. If there is no available tumor sample, biopsy will be performed to confirm the diagnosis.

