2.4 BASELINE EVALUATION

Tests done at screening do not need to be repeated on baseline if performed in designated time frame.

Within 28 days prior to first dose:

- CT or PET of chest, abdomen and pelvis (or MRI abdomen)
- Electrocardiogram
- HLA phenotype (any time prior to first dose)
- Optional tumor biopsy for research

Within 7 days prior to first dose:

- History and physical exam with vital signs

Within 72 hours prior to first dose:

[figure not shown]
- Serum or urine pregnancy test for female participants of childbearing age (in the absence of prior hysterectomy).

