3.6.1 Criteria for Removal from Protocol Therapy

Treatment may continue until one of the following criteria applies:

- Disease progression (per immune-related response criteria).
- Intercurrent illness that prevents further administration of treatment
- Unacceptable toxicity as defined in section **3.4**
- Participant requests to be withdrawn from active therapy
- General or specific changes in the patient's condition render the patient unacceptable for further treatment in the judgment of the investigator
- Delayed recovery from toxicity that prevents re-treatment in ≤ 28 days of scheduled therapy
- Investigator discretion
- Positive pregnancy test

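### No pregnancy test is scheduled after baseline, although a positive test ends therapy: a low-severity patient-safety gap in the study calendar

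*Combined protocol and SAP*

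**What the plan says.** Section 2.2 requires at screening a "Serum or urine pregnancy test for female participants of childbearing age", unless she has had a hysterectomy. Section 2.4 repeats the test under the heading "Within 72 hours prior to first dose". The calendar in section 3.5 agrees: its row "Serum or urine pregnancy test" carries a mark under Screening and under Baseline and nowhere else. Footnote 4, attached to that row, only allows a screening test done in the right time frame to stand in for the baseline or Cycle 1 Day 1 test.

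Section 3.6.1 lists "Positive pregnancy test" among the events that end protocol therapy. Pregnancy is also an exclusion at entry (2.1.2.17). Section 2.1.1.11 says that the combination's effects on the fetus are unknown, requires contraception until up to 120 days after the last dose, and tells a woman who is or may be pregnant to inform her physician at once.

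**The concern.** The entry criterion on pregnancy has scheduled tests behind it. The matching criterion for stopping treatment has none. Treatment is long: six three-week cycles of the combination, then pembrolizumab alone every three weeks until progression. A site that followed the calendar exactly could keep dosing through a pregnancy that neither the woman nor the examiner yet suspects. What is at stake is the safety of a participant and a fetus, not the validity of the trial's result.

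**Working it through.** No figure in the plan is to be reproduced here. The check is a reading of the calendar against the text, followed by a count of doses.

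**1. The calendar row.** Of the six columns, Screening and Baseline are marked. Cycles 1-6, Cycle 7 to PD, end of treatment and Follow-Up are blank. That is 2 of 6 columns, both before treatment.

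**2. Could a test be hidden elsewhere?**
- The chemistry panel in footnote 12 is "Electrolytes, BUN, creatinine, AST, ALT, total and direct bilirubin, calcium, phosphorus, albumin, magnesium, uric acid, amylase". It contains no pregnancy assay.
- No other footnote adds a test, and no other section schedules one on treatment.
- The item missing from the extracted text of section 2.4 falls under the 72-hour pre-treatment heading, so it cannot be an on-treatment test.
- Neighbouring rows show their marks in the treatment columns, so the blank cells do not look like a table-reading fault.

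**3. What does run on treatment?** Physical examination and "Adverse event evaluation" are marked in both treatment columns. Imaging follows footnote 6: "Restaging scans every 9 weeks +/- 7 days". Any of these may raise suspicion, but none is a pregnancy test.

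**4. Dose count.** Inputs: CAPOX every 3 weeks for 18 weeks (3.1), and pembrolizumab on Day 1 of every cycle (3.2).
- Day 1 doses with CAPOX: 18 / 3 = 6, nominally at weeks 0, 3, 6, 9, 12 and 15.
- Day 1 doses per imaging interval: 9 / 3 = 3.

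| Schedule | Day 1 doses with a scheduled test before them | Added assays, cycles 2-6 |
|---|---|---|
| As planned | week 0: 1/6 = 17% | 0 |
| Also at each 9-weekly restaging | weeks 0 and 9: 2/6 = 33% | 2 - 1 = 1 |
| Before each dose | 6/6 = 100% | 6 - 1 = 5 |

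From cycle 7 the plan covers no dose, 9-weekly testing would cover one in three, and testing before each dose would cover all.

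**5. What the count means.** It describes how far the schedule covers the doses. It measures neither exposure nor harm. The documents do not say how many women of childbearing age will enrol. They only cap accrual at 19 (section 8), so an absolute risk cannot be computed.

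**The case against.** The best defence is that nothing in the plan is contradictory. A reader might infer that sections 3.5 and 3.6.1 conflict, but they do not. Section 3.6.1 lists events that end therapy and does not promise a scheduled test for each. Intercurrent illness, on the same list, is also found clinically. The plan has layers: exclusion at entry, a test just before the first dose, mandatory contraception, immediate reporting, and examination every cycle. A test for cause can trigger the criterion at any time, and the list also allows investigator discretion. How often to repeat the test is then a matter of intensity, in a trial of at most 19 patients that may stop at 10.

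Much of this stands. It removes any charge of inconsistency and keeps the severity low. What remains is that patient report works only once the woman knows or suspects, that an unscheduled test depends on someone thinking of it, and that the stopping criterion is itself worded around a test result.

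A fair second objection is that serial testing brings false positives. As section 3.6.1 is worded, one positive result meets the criterion, so more tests without a confirmation step could remove a patient wrongly. That objection also stands, and the fix has to meet it.

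**Conclusion.** The gap is real and small. No dose after cycle 1 has a scheduled pregnancy test before it: five of the six combination doses, and every later pembrolizumab dose. The blank cells are certain; the size of the consequence is not known.

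Two stronger readings are tempting, and the documents support neither. The first is that a given number of doses would reach an unrecognised pregnancy. That would need the time to recognition without testing and the time until a test turns positive, and neither is in the documents. The second is that pre-dose testing would close the risk. It would not undo exposure already given in the cycle of conception: capecitabine runs for 14 days per cycle, and section 1.2.7 cites data suggesting that pembrolizumab's target engagement lasts more than 21 days.

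The point has no bearing on the 5-month progression-free endpoint, the two-stage design's error rates or the sample size. It is worth making because the correction is cheap.

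**What to change.** In the pregnancy-test row of section 3.5, mark a serum or urine test before each dose in the Cycles 1-6 and Cycle 7 to PD columns. Apply it to the population that sections 2.2 and 2.4 already define: female participants of childbearing age without prior hysterectomy. Attach footnote 13, "Within 48 hours prior to study drug", which already governs the blood count and chemistry in those columns. A serum test can then use the existing draw. The baseline test serves cycle 1.

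In section 3.6.1, qualify "Positive pregnancy test" so that it must be confirmed by a repeat test, with dosing held until the result is known.

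The cost is five added assays per eligible woman over cycles 2-6 and one per three-week cycle afterwards. No added visit is needed, because pre-dose laboratory work is already scheduled. A positive result would occasionally cause a short hold while it is confirmed. Section 3.2 lets a cycle start up to 3 days either side of its planned day, so a prompt repeat test may fit within that window. Testing only at restaging would be cheaper but leaves two doses in three without a test before them.
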